9.9.6 Pulmonary function tests - Spirometry

The following summary displays are provided by treatment group, all based on the SAF:

- Treatment-emergent FEV1, FVC, FEV1/FVC, %predFEV1, and %predFVC including absolute and percent change from baseline, as described in Section 5.5.13.1, are summarized descriptively, by parameter and visit. Except for ‘Baseline’, ‘Last on treatment’ and ‘Day-30 follow-up’, only treatment-emergent results from nominal scheduled visits are included; premature EOT visit is mapped to a scheduled visit [see Section 11.3].
- Number and percentage of subjects with any occasion of treatment-emergent low spirometry values as defined in Section 5.5.13.1 are presented. Percentages are based on the number of subjects with at least one treatment-emergent result available for the corresponding parameter;

All spirometry results are listed by treatment group and visit based on the SCR. A listing of spirometry data in subjects with treatment-emergent decrease ≥ 0.2 L or $\geq 12\%$ in FEV1 (or FVC) is also presented.

9.9.7 Columbia Suicide ideation or behavior

Suicidal Ideation, Suicidal Behavior or Self-Injurious Behavior without Suicidal Intent will be listed for each patient, at each assessment visit on the SCR. Events occurring during the period up to EOT + 15 days (treatment-emergent period) will be flagged.

Number (%) of subjects with suicidal ideation (overall and by category), suicidal behavior (overall and by category), suicidal ideation score ≥ 4 or suicidal behavior and/or self-injurious behavior without suicidal intent will be tabulated by treatment group up to EOT + 15 days (worst outcome). Analyses will be based on subjects in the SAF who have at least one treatment-emergent eC-SSRS[®] measurement available.

For subjects who have in addition a baseline eC-SSRS[®] assessment available shifts from baseline (maximum score from pre-treatment recent history) to the worst reported outcome (the maximum score) up to EOT + 15 days will be tabulated by treatment group to demonstrate any changes in Suicidal Ideation and Suicidal Behavior score categories.

All eC-SSRS[®] data will be presented in a listing on SCR.

9.10 Analysis of pharmacodynamic variables

9.10.1 Total lymphocyte counts

Descriptive analyses of lymphocyte data are described in Section 9.9.5. Only lymphocyte counts from central laboratory, irrespective of whether obtained at a scheduled or unscheduled visit, are included in any of the below described analyses.

For each subject in the SAF, the nadir (i.e., lowest) treatment-emergent lymphocyte value (up to EOT + 15 days) is summarized by means of frequency counts and percentages based on the categories specified in Section 5.6.

Frequency counts and percentages will be presented for the number of subjects with:

- Total lymphocyte counts $< 0.5 \times 10^9/L$ and $> 50\%$ decrease from baseline at Week 4, maintained at all visits for the next 24 weeks, where the denominator for percentages is the number of subjects with a total lymphocyte count at all scheduled visits for the next 24 weeks;
- Total lymphocyte counts $< 0.5 \times 10^9/L$ at any visit after Week 4 and $> 50\%$ decrease from Week 4, maintained at all visits for the next 24 weeks, OR total lymphocyte count $< 0.5 \times 10^9/L$ at any visit after Week 4 and $> 50\%$ decrease from Week 4, discontinuing for any reason within 24 weeks, with decrease maintained for remaining scheduled study visits, where the denominator for percentages is the number of subjects with a total lymphocyte count $< 0.5 \times 10^9/L$ and $> 50\%$ decrease from Week 4 at any visit after Week 4.

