5.6 Pharmacodynamic variables

5.6.1 Total lymphocyte counts

The main PD marker is total lymphocyte count, which is measured as part of the hematology test from central laboratory. Absolute and change from baseline counts are derived, as described in Section 5.5.12.

Total lymphocyte counts are further categorized into the following categories:

- $< 0.2 \times 10^9/L$;
- $\geq 0.2 \times 10^9/L - < 0.5 \times 10^9/L$;
- $\geq 0.5 \times 10^9/L - < 0.8 \times 10^9/L$;
- $\geq 0.8 \times 10^9/L - < 1.0 \times 10^9/L$;
- $\geq 1.0 \times 10^9/L$.

For each subject in the SAF, the nadir (i.e., lowest) treatment-emergent lymphocyte value (up to EOT + 15 days) is flagged.

Subjects who have a value after Visit 5 (Week 4) (scheduled or unscheduled) which is both $< 0.5 \times 10^9/L$ and represents a decrease from Week 4 $> 50\%$, and which is maintained at all visits (scheduled or unscheduled) for the next 24 weeks, will be flagged.

For example, if a subject has a value of $0.9 \times 10^9/L$ at Visit 5 (Week 4), then a value of $0.4 \times 10^9/L$ at Visit 6 (Week 12), a value of $0.35 \times 10^9/L$ at Visit 7 (Week 24) and a value of $0.4 \times 10^9/L$ at Visit 8 (Week 36), then the subject will be flagged as meeting the above criterion.

Subjects who have a value after Visit 5 (Week 4) (scheduled or unscheduled) which is both $< 0.5 \times 10^9/L$ and represents a decrease from Week 4 of $> 50\%$, and who discontinue treatment within 24 weeks, will be flagged separately if this decrease is maintained at their remaining study scheduled visits, where EOT and FU are considered to be scheduled visits.

Total lymphocyte counts from central laboratory are flagged for analysis according to their sample dates as 'Baseline', 'Last on treatment' and 'Day-30 follow-up' following the rules described in Section 5.5.1 and Section 11.4.

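### The first lymphocyte row in SAP 9.10.1 measures the fall from baseline at Week 4, which matches no flag in 5.6.1, and the second row's percentage is persistence among cases rather than incidence

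*SAP*

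**What the plan says.** Section 5.6.1 names total lymphocyte count as the main pharmacodynamic marker and derives two subject-level flags. The first needs a value after Visit 5 (Week 4) that is below 0.5 × 10⁹/L "and represents a decrease from Week 4" of more than 50%, "and which is maintained at all visits (scheduled or unscheduled) for the next 24 weeks, will be flagged". The second covers subjects with the same fall who stop treatment within 24 weeks; they "will be flagged separately if this decrease is maintained at their remaining study scheduled visits". A worked example follows for the first flag: 0.9 at Week 4, then 0.4, 0.35 and 0.4 at Weeks 12, 24 and 36. The SAP concludes: "then the subject will be flagged as meeting the above criterion".

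Section 9.10.1 then asks for counts and percentages in two rows.

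- **Row 1:** below 0.5 with a more than 50% "decrease from baseline at Week 4, maintained at all visits for the next 24 weeks". Its percentage is taken over those who have a count at every planned visit in that window.
- **Row 2:** below 0.5 and more than 50% below Week 4 at any visit after Week 4, either sustained for 24 weeks or followed by discontinuation within 24 weeks with the fall held. The denominator is subjects who had such a value at any visit after Week 4.

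Section 5.5.1 defines baseline for safety variables as the last valid assessment before dosing began. The lymphocyte alert in Appendix C, Table 9 also takes the Week 4 count as its reference for a percentage fall.

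**The concern.** Row 1 stands where a reader expects the sustained flag, but it changes both the reference (pre-dose baseline instead of Week 4) and the time of the fall (at Week 4 instead of after it). A programmer working from 5.6.1 and one working from 9.10.1 would fill the row with different subjects. Row 1 describes people already low at Week 4 who stay low. The flag describes people whose count drops further after Week 4.

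Row 2 raises a separate problem. Its numerator is a subset of a group defined by having met the threshold after randomization, and that group is its denominator. The percentage answers how often a fall persists once it has occurred. Set side by side by arm, it is easily read as the risk of sustained decline, which it is not.

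**Working it through.** **Inputs.** Thresholds, the worked example and the row definitions are from SAP 5.6.1 and 9.10.1; the baseline definition is from 5.5.1; 136 randomized subjects is from Sections 1 and 2. Percentage fall = (reference − value) / reference. Counts are in 10⁹/L.

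**1. The SAP's own example against the flag.** Reference is Week 4 = 0.9.

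- Week 12: (0.9 − 0.4)/0.9 = 55.6%
- Week 24: (0.9 − 0.35)/0.9 = 61.1%
- Week 36: (0.9 − 0.4)/0.9 = 55.6%

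All values are below 0.5, all falls exceed 50%, and Week 12 to Week 36 spans 24 weeks. The subject is flagged, as the SAP says.

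**2. The same subject in row 1 as written.** The criterion must be met at Week 4. The Week 4 value is 0.9, which is not below 0.5, so the subject is not counted whatever the baseline. In row 2 the subject is counted.

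**3. A looser reading of row 1.** Suppose the values after Week 4 were compared with the pre-dose baseline. The example subject is then counted for assumed baselines of 0.9, 1.0, 1.5 or 2.0, but not for 0.8, where (0.8 − 0.4)/0.8 is exactly 50%. The answer then depends on a value the example does not give.

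**4. The converse case (assumed values).** Baseline 1.2, Week 4 0.45, then 0.4 throughout.

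- Fall from baseline at Week 4: (1.2 − 0.45)/1.2 = 62.5%. Later values of 0.4 are 66.7% below baseline. Counted in row 1.
- Fall from Week 4: (0.45 − 0.4)/0.45 = 11.1%. Not flagged under 5.6.1.

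In general, a row 1 subject has a Week 4 value below 0.5 and so can meet the flag only with later values below 0.5 × 0.5 = 0.25. The two definitions overlap little.

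**5. Row 2's denominator (hypothetical counts).** Suppose 4 placebo and 20 ponesimod subjects met the threshold, and the fall persisted in 3 and 10. Assume 136/2 = 68 evaluable subjects per arm.

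| | Placebo | Ponesimod |
|---|---|---|
| Row 2 percentage | 3/4 = 75% | 10/20 = 50% |
| Incidence of a persistent fall | 3/68 = 4.4% | 10/68 = 14.7% |

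The two percentages point in opposite directions.

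**The case against.** A reader might infer that the flagged criterion is not tabulated at all. The document does not support that: row 2 is the union of both 5.6.1 flags on the Week 4 reference. What is missing is a row for the sustained flag alone.

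A reader might also infer that row 1 is a slip for a fall from Week 4. That is plausible but not shown. Row 1's denominator suits a fixed Week 4 anchor, because the following 24 weeks then have a start date for every subject, case or not. If the row were reworded to any visit after Week 4, that window would have no start date for non-cases. Row 1 may therefore be a deliberate summary of early, lasting lymphopenia, which the Week 4-relative flag would mostly miss. It can be computed without a named flag, and because it requires 24 weeks' persistence it is not merely the initial on-drug fall. This part of the objection stands, and a fix should not simply overwrite the row.

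On denominators, persistence among cases is a legitimate descriptive quantity, it is explicitly defined, and the counts are printed beside it, so a careful reader could see 3 against 10. Row 1's denominator does not have this defect, since it is not limited to subjects who met the threshold. A wider denominator would also admit subjects without 24 weeks of later counts, which matters in a study stopped early. That cost is real and calls for disclosure.

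Finally, lymphocyte decline is also shown through nadir categories, by-visit changes, marked abnormalities and listings. That limits the consequence but does not reconcile the two sections.

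**Conclusion.** The point holds as a minor inconsistency. Row 1 has no derivation in 5.6.1 and departs from the Week 4 reference used there, in row 2 and in the laboratory alert. It excludes the SAP's own flagged example, and the sustained flag on its own is never reported. Whether row 1 is a slip or an intended but underived summary cannot be settled from the document; either way the SAP needs an edit.

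Row 2's percentage measures persistence among subjects selected after randomization and should not be compared between arms as a risk. The reversal shown rests on invented counts and an assumed even split of 68 per arm. It shows what can happen, not what the data contain.

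The effect is limited to one untested descriptive table in a synoptic report. No efficacy result depends on it.

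**What to change.** 1. In 9.10.1, tabulate the 5.6.1 sustained flag as its own row: below 0.5 × 10⁹/L and more than 50% below Week 4 at any visit after Week 4, maintained for 24 weeks. Keep the combined row as well.
2. If the baseline-at-Week-4 row is intended, keep it under a separate label as early lymphopenia and add its derivation to 5.6.1. If it is not intended, remove it.
3. For the flag rows, give percentages of safety-set subjects with a Week 4 count and at least one later count, and state by arm how many of them lack 24 weeks of later counts.
4. Retain the persistence percentage only if it is labelled as persistence among subjects who met the threshold.

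The cost is SAP wording and a small change to one table program. No new data are needed.

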9.10.2 Lymphocyte subsets

All collected parameters from the T cell lymphocyte subset will be presented descriptively, with absolute values, as well as absolute and percent change from baseline values presented, using the T cell lymphocyte subset analysis set.

All collected parameters from the B cell lymphocyte subset will be summarized in the same way, using the B cell lymphocyte subset analysis set.

10 GENERAL STATISTICAL METHODOLOGY

This section describes in general terms the statistical models and methods applied.

10.1 Statistical methodology for count data

Count data will be analyzed assuming data is negative binomially (NB) distributed.

A generalized linear model with NB distribution will be assumed.

- t_j denotes the length of observation for subject j .
 Y_j denotes the counts of interest for subject j during t_j .
 μ_j denotes the mean of the NB distribution of Y_j .

The mean for the distribution of the ARR for subject j , denoted by μ_j/t_j , will be modeled by the following equation:

$$\log(\mu_j/t_j) = \mathbf{x}'_j \boldsymbol{\theta}, \text{ i.e., } \log(\mu_j) = \mathbf{x}'_j \boldsymbol{\theta} + \log(t_j), \text{ where}$$

- \mathbf{x}_j is the vector denoting study treatments and covariates for subject j
 $\boldsymbol{\theta}$ is the vector of unknown fixed-model parameters.

The SAS code for the NB model with 95% CI is as follows (considered “draft” until fully validated at analysis stage):

```
proc genmod data=ADREL;
  class Treat Strat Covar;
  model COUNTS = Treat Strat Covar / dist=negbin link=log
  offset = offset;
  lsmeans Treat / cl exp alpha = 0.05 OM;
  estimate 'Ponesimod - Placebo' || Treat 1 -1 / exp alpha = 0.05;
run;
```

The offset variable used will be specified per analysis (e.g., for ARR it is the log-transformed observation time, for total T1 lesions it is the log-transformed number of available MRI scans, ...).

The ‘LSMEANS’ statement will output the mean estimates for each of the treatment arms with 95% Wald CIs; the option OM ensures that the mean is derived for categorical covariates with weights as per observed marginal proportions.

The ‘ESTIMATE’ statement will output the rate ratio of the treatment effect with 95% Wald CIs. The direction of the estimate statement (governed by ‘1 – 1’ or ‘–1 1’) is chosen such that the rate ratio relative to placebo is provided (with rate ratio < 1 indicating ponesimod is better).

The number of covariates / stratification variables included in the model is different from analysis to analysis, and these are described in the respective analysis sections [see Section 9]. Interaction terms might be included in the model, depending on the analysis.

If the NB distribution is not considered to be appropriate (e.g., due to non-convergence), other distributions such as the Poisson and zero-inflated Poisson will be explored. For the Poisson distribution, a Poisson regression is conducted with model equation identical to the one for the negative binomial regression. The SAS code is as follows (considered “draft” until fully validated at analysis stage):

```
proc genmod data=ADREL;
  class Treat Strat Covar;
  model COUNTS = Treat Strat Covar / dist=poisson link=log
  offset = offset;
  lsmeans Treat / cl exp alpha = 0.05;
  estimate 'Ponesimod - Placebo' || Treat 1 -1 / exp alpha = 0.05;
run;
```

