9.6.2 Main analysis

The primary statistical analysis will be performed up to EOS on the FAS using a negative binomial (NB) regression model for confirmed relapses, with treatment as a factor and the binary stratification variable for EDSS category ($\text{EDSS} \leq 3.5$ versus $\text{EDSS} > 3.5$) from IRT included in the model. The model also includes an offset variable defined as the log of time on study (in years) from randomization up to EOS. The effect size will be measured by the relative reduction in the model estimated mean ARR for ponesimod compared to placebo including two-sided 95% Wald confidence interval (CIs).

Mean model-based estimates of the ARR (for confirmed relapses), by treatment arm, as well as 95% CIs are presented. A rate ratio comparing ponesimod 20 mg with placebo will be derived from the model including 95% CIs and the corresponding p-value. The dispersion parameter will also be displayed.

Descriptive summary statistics of the number of confirmed relapses as a continuous variable and the number of confirmed relapses in categories (0, 1, 2, 3, 4, ≥ 5), by treatment arm will be presented. The total cumulative number of confirmed relapses, as well as the total cumulative time on study (summed for all subjects) will also be displayed. From the total number of confirmed relapses and the total time on study the raw unadjusted ARR, by treatment arm, will be calculated and summarized.

The fit of the model will be assessed and other distributions such as the Poisson distribution will be considered in case of a lack of fit.

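### The Poisson fallback code in SAP 10.1 drops the OM option, so arm-level adjusted rates would be weighted differently from those of the negative binomial model (minor; rate ratio and p-value unaffected)

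*SAP*

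**What the plan says.** SAP section 9.6.2 fits a negative binomial model to confirmed relapses, "with treatment as a factor and the binary stratification variable for EDSS category" as the only other term besides the offset. Among the outputs, "Mean model-based estimates of the ARR (for confirmed relapses), by treatment arm, as well as 95% CIs are presented". The raw unadjusted ARR per arm is shown as well.

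Section 10.1 gives the SAS code. In the negative binomial block the arm means come from "lsmeans Treat / cl exp alpha = 0.05 OM", and the text explains that "the option OM ensures that the mean is derived for categorical covariates with weights as per observed marginal proportions".

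The fallback appears in two places. In 9.6.2, "other distributions such as the Poisson distribution will be considered in case of a lack of fit". Section 10.1 has a similar sentence, which promises to try alternatives and begins "If the NB distribution is not considered to be appropriate (e.g., due to non-convergence), other distributions such as the Poisson and zero-inflated Poisson will be". Where Poisson is chosen, 10.1 says that "a Poisson regression is conducted with model equation identical to the one for the negative binomial regression". Its code block repeats the CLASS, MODEL and ESTIMATE statements with only the distribution changed, but its LSMEANS line is "lsmeans Treat / cl exp alpha = 0.05" and stops there. Section 4, which lists changes and clarifications, does not mention a difference in weighting. Both code blocks are labelled draft until validated.

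**The concern.** The negative binomial block and its explanation fix what an adjusted arm-level rate means in this plan: an average over EDSS strata in the proportions observed in the trial. A switch of distribution should change the variance model and leave that meaning alone. As written it changes both. Without OM, LSMEANS gives each level of a class variable equal weight. That is software behaviour which the SAP does not state, but its own explanation of why OM is there implies it. With a two-level EDSS factor the weights become one half each.

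The arm-level ARRs and their confidence intervals are reported results of the primary analysis. The same code serves the MRI count models; section 9.7.3 names the Poisson fallback for CUALs explicitly. The choice of distribution is made after the fit has been seen, so the weighting of a reported rate would depend on the data for no stated reason.

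**Working it through.** The SAP states no figure on this point, so there is nothing to reproduce. The check compares the two code blocks and then works out what the missing option does.

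**Inputs from the SAP.** Main-effects log-link model with treatment and a two-level EDSS stratum (9.6.2, 10.1). OM present in the negative binomial code, absent in the Poisson code (10.1).

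**Inputs assumed.** p, the share of subjects with EDSS > 3.5, and RR, the event rate in the high stratum divided by that in the low stratum. Neither is in the SAP.

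**Formula.** The adjusted rate for an arm is exp(b0 + b_treat + w × ln RR), where w is the weight on the high stratum. With OM, w = p. Without OM, w = 0.5. Dividing the second by the first:

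factor = exp((0.5 − p) × ln RR) = RR^(0.5 − p).

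b0 and b_treat cancel, so the factor is the same in both arms. For example, p = 0.2 and RR = 1.5 give 1.5^0.3 = 1.129.

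**Factor (rate without OM ÷ rate with OM)**

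| p | RR 0.8 | RR 1.25 | RR 1.5 | RR 2 |
|---|---|---|---|---|
| 0.1 | 0.915 | 1.093 | 1.176 | 1.320 |
| 0.2 | 0.935 | 1.069 | 1.129 | 1.231 |
| 0.3 | 0.956 | 1.046 | 1.084 | 1.149 |
| 0.4 | 0.978 | 1.023 | 1.041 | 1.072 |

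The factor is exactly 1 when p = 0.5 or RR = 1.

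**Rate ratio.** Both arm rates are multiplied by the same factor, so their ratio is unchanged. The ESTIMATE statement uses only the treatment coefficient, so its confidence interval and Wald p-value do not involve w at all.

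**Numerical check.** One simulated data set of 136 subjects, with p = 0.206 and a fitted stratum ratio of 1.08, was analysed by Poisson regression. The ARRs (ponesimod / placebo) were 0.225 / 0.383 with OM and 0.230 / 0.392 without, about 2% higher. The formula gives 1.081^(0.5 − 0.206) = 1.023. The rate ratio was 0.588 both ways.

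**Arm-level confidence intervals.** These use the Poisson information matrix with assumed values of 100 subject-years per arm, a raw placebo ARR of 0.2 and a treatment rate ratio of 0.7. With p = 0.1 and RR = 1.25, the standard error of the placebo log ARR is 0.224 with OM and 0.299 without. The interval widens because equal weighting leans on a stratum with few subjects. With p = 0.4 and the same RR there is practically no change (0.224 both ways).

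**The case against.** The strongest reply is that nothing inferential moves. The primary Wald test, the rate ratio, the relative reduction and their intervals are the same with or without OM, and the raw ARR per arm is reported whatever model is used. The problem arises only if the fallback is used, and then only if the strata are unbalanced and EDSS predicts the event rate. Both code blocks are draft, and the intended weighting is written out in the same section. All of this stands and keeps the severity low. It does not remove the point: the explanation of OM sits beside the negative binomial code only, nothing extends it to other distributions, and a programmer who validates against the Poisson block as printed would reproduce the omission.

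A reader might also infer four stronger things, which the documents do not support:

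- *That the fallback would report the ARR of a population half of which has EDSS > 3.5.* Least-squares means average on the log scale. At RR = 2 a half-and-half population has 1.50 times the low-stratum rate, while the equal-weight mean is 2^0.5 = 1.41 times.
- *That OM estimates reproduce the raw ARR and only the fallback departs from it.* At p = 0.2 and RR = 2, with equal follow-up across strata, OM gives 2^0.2 = 1.149 times the low-stratum rate against a population mean of 1.20, about 4% low. The equal-weight value is about 18% high (1.414 / 1.20). OM is closer but not equal.
- *That the rates would always be overstated.* With RR below 1 and p below 0.5 they are understated.
- *That absolute ARR differences would be distorted.* Section 9.6.2 plans a relative reduction and a rate ratio, and no absolute difference.

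**Conclusion.** The inconsistency is real and can be read directly from section 10.1: two code blocks meant to differ only in distribution also differ in how the EDSS strata are weighted. If the Poisson fallback is used as printed, both arms' adjusted ARRs, and MRI lesion rates where those models fall back, change by RR^(0.5 − p), and their confidence intervals change too. Over the assumed range the factor is about 0.92 to 1.32. The upper end needs both a rare high-EDSS stratum and a doubled rate in it. The true size cannot be fixed from the SAP, because neither p nor RR is given, and it may be nil. Severity is minor, because the treatment comparison and its test are untouched.

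**What to change.** Add OM to the LSMEANS statement of the Poisson code in section 10.1. Add one sentence there stating that arm-level rates from any alternative count model, including zero-inflated Poisson, use the same observed-margin weighting of categorical covariates as the negative binomial model. The cost is one option and one sentence. No result of the planned negative binomial analysis changes, and with OM in both blocks the shift factor is 1.
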